2.1 Study Rationale

NFlection tested the efficacy of a topical formulation of a novel MEK inhibitor (NFX-179) in an *ex vivo* model by using human cutaneous neurofibroma explants. Dose dependent suppression of the shared biomarker, p-ERK, by NFX-179 [REDACTED] was observed in human cutaneous neurofibroma explants. P-ERK suppression was not observed in neurofibroma explants treated with the vehicle formulation.

Western Blot analysis of p-ERK level showed complete suppression of p-ERK by all three dosages of NFX-179 in the top sections of the explant and a dose dependent suppression in the bottom sections.

Taken together, these data clearly demonstrate that NFX-179 [REDACTED] can penetrate human epidermis and suppress p-ERK in human cutaneous neurofibroma explants.

The NFX-179-NF1-201 study of NFX-179 Topical Gel applied once daily for 28 days in subjects with cNF tumors demonstrated the safety and tolerability of concentrations up to [REDACTED] and the potential therapeutic benefit of NFX-179 Gel to treat NF1 by reducing cNF tumor volume based on early clinical and biomarker evidence.

This study is designed to evaluate the dose response and efficacy of 2 concentrations of NFX-179 Gel [REDACTED] after 182 days (26 weeks) of once-daily (QD) application in subjects with *NF1* tumors.

2.2 Background

2.2.1 Nonclinical Experience

NFX-179 was evaluated for effects on cardiovascular, respiratory, and central and peripheral nervous systems in safety pharmacology studies. NFX-179 was found to block the hERG channel current with an IC_{50} value of [REDACTED] μ M, which did not translate to any effect on the electrocardiogram (ECG) in the conscious dog. Doses achieving plasma levels of up to [REDACTED] ng/mL ([REDACTED] μ M) at 2 hours post dose were without effect on ECG intervals, heart rate, and blood pressure or on tidal volume and respiratory rate and minute volume. Effects of oral NFX-179 on neurological function were assessed in male and female rats dosed with up to [REDACTED] mg/kg on Day 1 of the 28-day rat oral toxicity study; there were no effects on central and peripheral nervous system function with an NFX-179 C_{max} of [REDACTED] ng/mL in males and females, respectively.

In the minipig, topical administration of [REDACTED] w/w NFX-179 Gel results in very low systemic

exposure to NFX-179 with mean C_{max} and AUC_{last} values (male and female combined) of [REDACTED] ng/mL and [REDACTED] ng.h/mL, respectively, while high levels of NFX-179 were attained in the dermis/epidermis layers of the skin (up to [REDACTED] ng/g).

In the Good Laboratory Practice (GLP) 28-day dermal toxicology/toxicokinetic (TK) study, NFX-179 Gel was applied to minipigs topically with an application density of [REDACTED] $\mu\text{L}/\text{cm}^2$ vs. [REDACTED] $\mu\text{L}/\text{cm}^2$) at up to [REDACTED] w/w. When measured 24 hours post dose after 28 days of administration, this dosing schedule resulted in high levels of NFX-179 in the dermis/epidermis layer of the skin related to the volume and concentration of the formulation applied while attaining relatively low levels of systemic exposure.

NFX-179 Gel was well-tolerated when applied dermally. There was sporadic and transient erythema, which was mostly graded as very slight (barely perceptible), with some episodes of well-defined erythema, and occasional but infrequent moderate erythema with occasional edema. There were no systemic effects at any dose level, including the highest dose level of [REDACTED] w/w NFX 179, equivalent to [REDACTED] mg/kg/day. The no observed-adverse-effect level (NOAEL) for this study was the lowest dose of [REDACTED] w/w applied to 10% body surface area (BSA) at [REDACTED] $\mu\text{L}/\text{cm}^2$, equivalent to [REDACTED] mg/kg/day.

In the GLP 13-week dermal toxicology/TK study in minipigs, multiple animals, particularly in Groups 4 (initially [REDACTED] mg/kg/day, [REDACTED] and 5 (initially [REDACTED] mg/kg/day, [REDACTED] were placed on dose holiday for irritation at the dose site. The dose volume was reduced twice, on Day 19 (males)/Day 14 (females) to [REDACTED] and [REDACTED] mg/kg/day, respectively, and Day 68 (males)/Day 63 (females) to [REDACTED] mg/kg/day, respectively. Following 91 days of dermal administration of NFX-179 Gel, there were no adverse systemic effects; however, animals at [REDACTED] mg/kg/day ([REDACTED] Group 4) and [REDACTED] mg/kg/day ([REDACTED] Group 5) did not receive sufficient doses to evaluate the systemic toxicity following 91 days. These dose levels/dose concentrations were considered not tolerated due to multiple dose holidays and the need for pain management. The NOAEL for both local and systemic toxicity was [REDACTED] mg/kg/day ([REDACTED] Group 3). At the NOAEL in males and females, respectively, mean C_{max} was [REDACTED] and [REDACTED] ng/mL and mean AUC_{0-24h} was [REDACTED] and [REDACTED] ng.hr.ng/mL.

Potential toxicities associated with increased systemic exposure were investigated in a GLP 28 day oral rat study where the NOAEL was [REDACTED] mg/kg/day with systemic exposures (C_{max} and

AUC_{0-24h}) of [REDACTED] and [REDACTED]-fold higher, respectively, for NFX-179 compared to plasma levels in the minipig following topical administration of a similar human equivalent dose. NFX-179 oral suspension was well tolerated in the rat at [REDACTED] mg/kg/day given orally with the spleen, liver, mesenteric lymph nodes, stomach, femur, ovaries, and skin/subcutis being the primary target organs for toxicity; the toxicities recorded at the NOAEL dose were either fully or partially reversible following a 14 day treatment-free period and were therefore considered non-adverse.

In the GLP 13-week oral toxicology/TK study in the rat, NFX-179 was well tolerated at dose levels of up to [REDACTED] mg/kg/day for 13 weeks, with toxicity limited to reductions in white blood cell counts in males at [REDACTED] mg/kg/day and red cell counts in females given [REDACTED] mg/kg/day, which were reversible following a 4-week treatment-free period. These findings correlated with increased incidence of adipocytes in the bone marrow and extramedullary haematopoiesis in the spleen at the end of the dosing period; however, as the peripheral blood changes were reversible, these microscopic findings were considered not to be adverse. The NOAEL was considered to be [REDACTED] mg/kg/day, equivalent to a C_{max} after 13 weeks of [REDACTED] or [REDACTED] ng/mL, and an AUC₀₋₂₄ of [REDACTED] or [REDACTED] ng.h/mL, in males and females, respectively.

NFX-179 was not mutagenic, clastogenic or aneugenic when evaluated in both in vitro and in vivo genetic toxicity tests. NFX-179 Gel was found to have no potential for skin sensitization, and there was no potential for eye irritation. NFX-179 showed high levels of light absorbance in the UV/Vis range, indicating that it has the potential to be phototoxic and photosensitizing.

Full details of the nonclinical studies for NFX-179 Gel are presented in the Investigator's Brochure.

2.2.2 Clinical Experience

NFlection Therapeutics, Inc. has completed the first-in-human (FIH) Phase 2a study. The NFX-179-NF1-201 study was a 28-day double-blind, randomized, vehicle-controlled, parallel-group Phase 2a study to determine the safety, tolerability, pharmacokinetics, and pharmacodynamics of NFX-179 Gel [REDACTED] compared with vehicle in 48

subjects with cNF tumors. NFX-179 Gel applied once daily for 28 days at the 3 concentrations evaluated was shown to be safe and well tolerated. No treatment-related TEAEs and no acneiform rash were reported. There were few reports of signs and symptoms on the local tolerability assessments and almost all were mild and transient. There were no clinically relevant changes in laboratory parameters, vital signs, or ECGs. NFX-179 Gel demonstrated statistically significant dose-dependent suppression of p-ERK in cNF tumors in the [REDACTED] Gel groups ([REDACTED] suppression, respectively) and a dose-related mean percent reduction in tumor volume at Day 28. Higher dose groups demonstrated a volume reduction that was correlated with p-ERK suppression.

Thus, in addition to demonstrating the safety and tolerability of concentrations up to [REDACTED] this study showed the potential therapeutic benefit of NFX 179 Topical Gel to treat NF1 by reducing cNF tumor volume based on early clinical and biomarker evidence.

Based on the results of the preclinical studies and NFX-179-NF1-201 Phase 2a study, the risk/benefit assessment supports evaluation of the [REDACTED] concentrations of NFX-179.

3 STUDY OBJECTIVES AND ENDPOINTS

The objectives of this study include the following:

Primary Objectives:

- To determine the effectiveness of each of two concentrations of NFX-179 Gel [REDACTED] compared with Vehicle Gel applied once daily (QD) for 182 days
- To determine the safety of NFX-179 for each active treatment group compared with the vehicle group after 182 days of QD treatment.

Efficacy Objectives:

- To determine the effect of NFX-179 Gel defined as the percent of responders after 182 days of treatment
- To determine the effect of NFX-179 Gel defined as the percent change in cNF volume after 182 days of treatment based on cNF volume derived from ruler measurements
- To determine the effect of treatment with NFX-179 Gel as the change from baseline in the Physician's Tumor Assessment after 182 days of treatment
- To determine the effect of treatment with NFX-179 Gel as the change from baseline in the Subject's Self-Assessment after 182 days of treatment.

Exploratory Efficacy Objective:

- To determine the effect of treatment with NFX-179 Gel as the change from baseline in the individual Patient Reported Outcome Measurements after 182 days of treatment

The endpoints being evaluated in this study include the following:

Safety endpoints:

- Safety of NFX-179 for each treatment group compared with the vehicle group after 182 days of QD treatment.

Efficacy endpoints:

- Primary Efficacy Endpoint:
 - Percent of responders, defined as at least a 50% reduction in cNF volume above the surrounding non-tumor skin determined from ruler measurements after 182 days of QD applications of NFX-179 Gel
- Secondary Efficacy Endpoints:
 - Percent change in cNF volume after 182 days of QD applications of NFX-179 Gel based on cNF volume derived from ruler measurements
 - Effect of treatment with NFX-179 Gel as the change from baseline in the Physician's Tumor Assessment
 - Effect of treatment with NFX-179 Gel as the change from baseline in the Subject's Self-Assessment
- Exploratory Efficacy Endpoint:
 - Effect of treatment with NFX-179 Gel as the change from baseline in each of the Patient Reported Outcome Measurements after 182 days of treatment

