9.3 Statistical Analyses

9.3.1 General Approach

All randomized and treated subjects will be assessed in analyses of safety and efficacy. Descriptive statistics will be produced on relevant screening and baseline data and on demographic characteristics. Safety and efficacy endpoints will be summarized descriptively by treatment (when applicable) and for all subjects combined and may be analyzed using appropriate parametric or nonparametric inference tests. Comparisons between NFX-179 treated cNFs and vehicle treated cNFs will also be performed as described below. Summaries and analyses will be based primarily on non-missing data.

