9.3.5.3 Endpoints

The safety endpoint is to determine the safety of treatment with NFX-179 Gel ([REDACTED] and [REDACTED] or Vehicle Gel applied QD for 182 days of treatment. The results of dermal safety and local tolerability assessments including pain/burning, itching, erythema, edema, scabbing/crusting, and vesiculation/erosion will be summarized by treatment group and visit. The evaluation of adverse events will be based on summaries and listings of adverse events by treatment group, as described below under Safety Analyses. If tumor independence is confirmed as discussed above, the primary efficacy endpoint will be a dichotomized analysis conducted on the proportion of tumors achieving a reduction from baseline volume of at least 50%. A Chi-square analysis at the tumor level will be performed as the primary analysis between vehicle and each active treatment group. Otherwise, if tumor independence is not confirmed, the primary efficacy endpoint will be analyzed at the subject level. The primary efficacy analysis will then be a dichotomized Chi-square Responder analysis at the subject level. It will be based on the proportion of subjects considered to be Responders, where a Responder is defined as a subject

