9.3.6 Safety Analyses

Subjects will be assessed for the occurrence of new and ongoing AEs. Descriptions of AEs will include the dates of onset and resolution (if resolved), maximum severity, seriousness, and action taken regarding the study drug, corrective treatment, outcome, and investigator's assessment of causality. All AEs will be recorded and classified using terminology from the Medical Dictionary for Regulatory Activities (MedDRA). All reported treatment-emergent AEs (TEAEs), defined as any AE with an onset on or after the date of first study drug application, will be summarized by treatment group, the number of subjects reporting TEAEs, system organ class, preferred term, severity, and relationship to study drug. When summarizing TEAEs by severity or relationship to study drug, each subject will be counted only once within a system organ class or a preferred term using the event with the greatest severity or causality, respectively, within each category. All reported SAEs will be summarized by treatment group, the number of subjects reporting SAEs, system organ class, preferred term, severity, and relationship to study drug.

All information pertaining to AEs noted during the study will be listed by subject and will include a verbatim description of the event as reported by the investigator, as well as the preferred term, system organ class, start date, stop date (if stopped), seriousness, severity, action taken regarding the study drug, corrective treatment, outcome, and relationship to the study drug. In addition, a listing of subjects who prematurely discontinued from the study due to AEs will be provided as well as a listing of subjects who reported an SAE.

Changes from baseline in safety laboratory values, local tolerability assessments, and vital sign measurements will be summarized with descriptive statistics for each treatment group at

all applicable study visits.

Shift tables will be presented for changes in safety laboratory values to summarize laboratory test results collected at all visits. Normal ranges established by the central laboratory will be used to determine the shifts. A listing of all out-of-range laboratory test results at any assessment time point will also be provided. Determination of clinical significance for all out-of-range laboratory values will be made by each investigator and included in the listing. In addition, a listing of all clinically significant laboratory test results will be provided.

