Other safety assessments, including vital signs, physical examination data and LTA data will be summarized by treatment group.

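### Safety of each concentration compared with vehicle is a primary objective, but the plan commits only to within-arm safety summaries and optional, unspecified tests, with no between-arm estimate or interval and no subject-level summary of local tolerability.

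*Combined protocol and SAP*

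**What the plan says.** Section 3 lists two primary objectives. The second is "To determine the safety of NFX-179 for each active treatment group compared with the vehicle group after 182 days of QD treatment". The safety endpoint in the same section restates it: "Safety of NFX-179 for each treatment group compared with the vehicle group after 182 days of QD treatment". Neither names a measure, an effect scale or a criterion.

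The analysis sections describe the following output.

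- **Adverse events, section 9.3.5.3:** "The evaluation of adverse events will be based on summaries and listings of adverse events by treatment group".
- **TEAEs, section 9.3.6:** they "will be summarized by treatment group, the number of subjects reporting TEAEs, system organ class, preferred term, severity, and relationship to study drug". SAEs are handled the same way. There are also listings of all AEs, of SAEs and of discontinuations due to AEs.
- **Changes from baseline, section 9.3.6:** laboratory values, "local tolerability assessments, and vital sign measurements will be summarized with descriptive statistics for each treatment group".
- **Laboratory values, section 9.3.6:** "Shift tables will be presented for changes in safety laboratory values", with listings of out-of-range and clinically significant results.
- **Remaining safety data, section 9.3.6:** "Other safety assessments, including vital signs, physical examination data and LTA data will be summarized by treatment group".

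The synopsis follows the same pattern. On inference, section 9.3.1 says that safety and efficacy endpoints "may be analyzed using appropriate parametric or nonparametric inference tests".

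**The concern.** A comparative primary objective should lead to a stated comparison. Here the reader of the study report will have three columns of results and no prespecified statement of how far each active arm differs from vehicle or how precisely that is known. With about 56 subjects per arm, columns that look alike are compatible with sizeable differences in harm. If differences are calculated later, the choice of measures and method will be made after the data are seen.

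Local tolerability is where this matters most. The only earlier clinical study described (section 2.2.2) lasted 28 days in 48 subjects, while treatment here lasts 182 days. The 13-week minipig study in section 2.2.1 needed dose holidays for irritation at the application site. Irritation is therefore a foreseeable harm, and its analysis is the least defined.

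**Working it through.** **1. What is committed, set against the objective.**

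| Place | Commitment | Active minus vehicle? |
|---|---|---|
| 3, objective and safety endpoint | Safety compared with vehicle | Asked for |
| 9.3.3 | List of safety domains | No contrast |
| 9.3.5.3, 9.3.6, synopsis | Counts, descriptive changes, shift tables, listings, all by arm | No |
| 9.3.2 | Separate comparisons of each active group with vehicle | Efficacy analyses only |
| 9.3.5.2 | Contrasts among the three groups | Placed under efficacy; purpose stated as detecting effectiveness |
| 9.3.1 | Inference tests on safety and efficacy endpoints | Optional; nothing named |
| 9.3.5.3, end | 95% confidence limits | Volume response against PROM response, not safety |

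Section 9.3.1 also announces comparisons of NFX-179-treated with vehicle-treated cNFs, to be described later. The later text describes such comparisons for efficacy only.

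**2. Local tolerability.** Section 7.1.3 scores 8 items (5 signs, 3 symptoms) from 0 to 3 on each of 10 Target cNFs at Visits 2 to 9. Section 8.1.1 makes worsening of these scores an AE only if study medication is interrupted or stopped, or other therapy is needed. Milder worsening is thus visible only in the tolerability tables, which are by arm and visit. Those tables cannot show how many subjects ever reached a given grade, because no rule reduces up to 10 tumors and several visits to one value per subject.

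**3. The plan's own figures.** Section 9.1 gives about 168 randomized and at least 150 completing; section 9.2 gives 1:1:1. So 168/3 = 56 randomized and 150/3 = 50 completing per arm, an implied loss of 1 - 150/168 = 10.7%. The stated power of at least 90% concerns the efficacy responder rates, which are redacted, so it cannot be reproduced. No precision or power is stated for safety.

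**4. Illustration of precision at 56 per arm.** All counts below are assumptions.

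*12/56 active, 6/56 vehicle.* Difference = 0.2143 - 0.1071 = 0.1071.
- Wald: SE = sqrt[(0.2143 × 0.7857 + 0.1071 × 0.8929)/56] = 0.0687. The interval is 0.1071 ± 1.96 × 0.0687, or -2.7 to +24.2 points.
- Miettinen-Nurminen: the limits are the values d at which |0.1071 - d| / sqrt{[pA(1-pA)/56 + pV(1-pV)/56] × 112/111} = 1.96, where pA and pV are the maximum likelihood estimates restricted to pA - pV = d.
  - At d = 0.248, pA = 0.3216 and pV = 0.0736. The denominator is 0.0718 and the ratio 0.1409/0.0718 = 1.96.
  - At d = -0.031, pA = 0.150 and pV = 0.181. The denominator is 0.0706 and the ratio 1.96.
  - The interval is -3.1 to +24.8 points.

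*6/56 active, 3/56 vehicle.* Difference = 0.0536. By the same equation:
- At d = 0.170, pA = 0.204 and pV = 0.034. The denominator is 0.0593 and the ratio 1.96.
- At d = -0.055, pA = 0.067 and pV = 0.122. The denominator is 0.0553 and the ratio 1.96.
- The interval is -5.5 to +17.0 points.

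A library routine whose restricted estimates are slightly off returns -3.1 to +24.5 and -5.4 to +16.8 for these two cases. The gap of up to 0.3 points does not affect the conclusion.

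*Range.* With Newcombe intervals, 0/56 against 0/56 gives 0 (-6.4 to +6.4), and 28/56 against 22/56 gives +10.7 (-7.5 to +28.0). Half-widths run from about 6 to 18 points.

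**5. Why tests would not fill the gap.** At 56 per arm and two-sided 0.05, power is about 32% for 10% against 20% and 43% for 20% against 35% (assumed rates). A non-significant test would say little.

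**The case against.** The strongest reply is that side-by-side incidence in a randomized, double-blind trial with a concurrent vehicle arm already is a comparison with vehicle. Descriptive safety reporting is common in phase 2, no safety hypothesis or margin is stated, and anyone can calculate a risk difference from subject counts and denominators. On this view, intervals are a reporting preference and nothing is irretrievably lost.

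Much of this stands for AE counts, and it is why estimation without p-values is the proportionate remedy. It does not stand for local tolerability, where the planned tables do not contain the subject-level counts. Nor does it explain why this protocol words its primary objective and endpoint as comparisons.

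Three stronger readings should be resisted.

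- A reader might infer that the plan offers nothing but event counts and leaves the objective to visual impression. It does not: change-from-baseline summaries, shift tables and several listings are committed, and each arm's proportion is itself an estimate.
- A reader might infer that safety comparisons are ruled out. Section 9.3.1 permits tests; they are optional and unspecified, and section 9.3.6 does not take them up.
- A reader might infer that the trial is too small for its safety objective. The documents set no safety target against which to judge that, and no sample-size change follows.

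**Conclusion.** The point holds. A primary objective and its endpoint are comparative, and no committed analysis yields an active-minus-vehicle safety estimate with an interval. For local tolerability the gap is more than presentation, since no subject-level summary is defined and milder worsening does not reach the AE tables.

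The practical size is the uncertainty left unstated: at 56 per arm, roughly 6 to 18 points either side of an observed difference. That range rests on assumed counts, because the documents give no AE rates for this trial, and on all 56 randomized subjects per arm entering the Safety Population; fewer would widen it. Efficacy inference, data collection and sample size are unaffected. The change should be made before unblinding, so that measures and method are fixed in advance.

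**What to change.** In section 9.3.6 and the synopsis, for the Safety Population, report for each concentration minus vehicle the risk difference with a 95% Miettinen-Nurminen interval and no p-value, for this list:

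- any TEAE;
- any related TEAE;
- any severe TEAE;
- any TEAE leading to interruption or discontinuation of study medication;
- the AEs of special interest in section 8.1.4 (kidney, liver, coagulation, immune system), with the qualifying preferred terms listed beforehand;
- for each of the 8 local tolerability items, the subject's worst post-baseline grade on any Target cNF, dichotomized at a prespecified grade (for example 2 or more). State whether the post-application assessment at Visit 2 counts.

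Add that the intervals are descriptive and not adjusted for multiplicity, and that an interval including zero does not show absence of a difference.

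The cost is some extra table columns and one derived variable per tolerability item, all from data already collected. With the four special-interest groups reported separately there are 4 + 4 + 8 = 16 measures, or 32 intervals for two concentrations. Many will be wide, and at nominal 95% coverage about 32 × 0.05 = 1.6 would be expected to exclude zero with no true difference, which is why the descriptive label is needed.

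A lesser alternative is to reword the safety objective and endpoint as descriptive. That would remove the mismatch, but the subject-level tolerability summary would still be needed.
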